# 5.1.2 Secondary Objectives

- To characterize the PK of TAK-020 following single and multiple oral doses.
- To characterize the PD of TAK-020 following single and multiple oral doses.

## 5.2 Endpoints

## **5.2.1 Primary Endpoints**

The primary safety endpoints include the number and percentage of subjects who:

- Experience at least 1 treatment-emergent adverse event (TEAE).
- Meet the Takeda Development Center, Inc. (TDC) markedly abnormal values (MAV) criteria for safety laboratory tests at least once postdose.
- Meet the TDC MAV criteria for vital sign measurements at least once postdose.
- Meet the TDC MAV criteria for safety electrocardiogram (ECG) parameters at least once postdose.

# 5.2.2 Secondary Endpoints

The secondary endpoints will be the following PK parameters of TAK-020:

- Maximum observed plasma concentration (Cmax).
- Time of first occurrence of  $C_{max}$  ( $t_{max}$ ).
- Area under the plasma concentration-time curve from time 0 to the time t (AUCt).
- Area under the plasma concentration-time curve from time 0 to infinity  $(AUC_{\infty})$ .
- Area under the plasma concentration-time curve during a dosing interval, where tau ( $\tau$ ) is the length of the dosing interval (AUC $\tau$ ).
- Terminal disposition phase half-life  $(t_{1/2z})$ .
- Apparent clearance after extravascular administration (CL/F).
- Apparent volume of distribution during the terminal phase after extravascular administration (Vz/F).

- Total amount of drug excreted in urine from time 0 to time t (Aet).
- Fraction of drug excreted in urine (fe).
- Renal clearance (CLR).

# 5.2.3 Exploratory Endpoints

# 6.0 STUDY DESIGN AND DESCRIPTION

# 6.1 Study Design

This is a phase 1, randomized, double-blind, placebo-controlled, single and multiple-dose study in healthy volunteers. The study is comprised of 2 parts, each with multiple cohorts and is presented in the Study Schematic below. The study population for each part will be composed of healthy subjects aged 18 to 55 years, inclusive, who weigh at least 45 kg, and have a body mass index (BMI) between 18 and 32 kg/m^2, inclusive, at Screening and Day -1.

SRD=single-rising dose, MRD=multiple-rising dose.

Part 1: SRD

This part will comprise a maximum of 9 cohorts. Each cohort will comprise of 8 randomized subjects, with 6 receiving TAK-020 and 2 receiving placebo in the fasted state. Sentinel dosing will be used for Cohort 1 with only 2 subjects dosed on the morning of Day 1 (1 receiving TAK-020 and 1 receiving placebo). The remaining subjects will be dosed following agreement with the investigator and Takeda after reviewing 24-hour postdose safety (adverse events [AEs], vital signs, 12-lead ECGs) and tolerability data. Sentinel dosing will not be necessary for other cohorts provided that exposure is observed in  $\geq$ 4 subjects receiving active treatment and in agreement with the investigator and Takeda, otherwise sentinel dosing in the subsequent cohort will be required.

TAK-020 will be orally administered as a solution with a starting dose of 0.1 mg for Cohort 1. Dosing for the subsequent cohorts will only occur after review of the safety, tolerability, and minimum 24-hour PK data from the previous cohort. For each dose escalation, exposures may be increased by a maximum of 5-fold for Cohorts 2-4 and a maximum of 2-fold for Cohorts 5 to 9. Doses may also be decreased as appropriate.

# Part 2: MRD

TAK-020 will be orally administered as a solution. The dose to be used in each cohort will be selected based on data from Part 1 of the study and from the previous cohort in Part 2.

# 2) MRD Evaluation

The first cohort for the MRD will receive a dose of 3.75 mg, with a predicted exposure at steady state estimated to be below the NOAEL rat (63 ng\*h/mL). The cohort may be initiated when the

TAK-020	
Study No. TAK-020-1001	Page 26 of 101
Protocol Incorporating Amendment No. 4.0	27 March 2017

acceptable safety and tolerability have been collected in the SRD. The predicted steady state exposure in the first MRD cohort will be approximately 10-fold lower than the highest predicted steady state exposure determined from the SRD data. The MRD will comprise a maximum of 7 cohorts, each cohort with 8 subjects randomized with 6 receiving TAK-020 and 2 receiving placebo. In each successive cohort after the first, the dose increments will increase the predicted exposures by no more than 2-fold. The predicted steady state exposure in the MRD will not exceed the maximum exposure observed in the SRD.

A schematic of the study design is included as Figure 6.a. A schedule of assessments is listed in Appendix A.

## Figure 6.a Schematic of Study Design

### **Study Schematic for Part 1**

Screening	Check-in	Dose	Check-out	Follow-up (a)
Day -28 to -2	Day -1	Day 1	Day 5	Day 14 (±2)

(a) A phone call is planned but individual subjects may be asked to return to the unit at this time if abnormal clinical safety laboratory values are obtained at Check-out or TEAEs have not resolved at Check-out.

## **Study Schematic for Part 2**

Screening	Check-in	Dose	Washout	Dose	Check-out	Follow-up (a)
Day -28 to -2	Day -1	Day 1	Day 2	Days 3-9	Day 10	Day 17 (±2)

(a) All subjects will return to the unit and complete hematology, serum chemistry, renal biomarkers and pharmacodynamic tests, vital signs, concomitant medications, and AE assessment.

## 6.1.1 Dose Escalation

The dose escalation scheme is shown in Figure 6.b. All decisions concerning dose escalation will be made by Takeda (at a minimum, the clinical science representative(s) and pharmacovigilance physician) and the principal investigator (PI). Additionally, Takeda and the PI may jointly decide to not escalate the dose for a particular cohort, but rather administer the same or a lower dose level to the next cohort.

The AUC24 will be calculated for each subject and subsequently the geometric mean of AUC24 will be determined for each cohort (excluding placebo). Dose escalation will proceed to a dose level that is predicted to give a TAK-020 unbound AUC of (19.8 ng\*h/mL) approximately 2-fold higher than the unbound AUC of the rat LOAEL.

There will be a minimum period of 5 days between each dose escalation to allow for review of safety, tolerability and PK data. The blind of the PK data will remain intact during these reviews by using an alias number as the subject identifier instead of randomization sequence number for each subject.

For each dose level administered/completed cohort, the PI and Takeda will carefully review the available blinded safety, tolerability and blinded PK data (if data is available in time for the planned review). They will determine whether dosing should stop or continue (and, if continue, at what dose, including whether to repeat the previous dose), whether additional sequential dosing

TAK-020	
Study No. TAK-020-1001	Page 27 of 101
Protocol Incorporating Amendment No. 4.0	27 March 2017

should be implemented in future cohorts or whether the blind should be broken to identify whether the subjects received TAK-020 or placebo. In the next cohort (Part 1), exposures may be increased by a maximum of 5-fold as long as the predicted exposure will be below that at the NOAEL in the most sensitive nonclinical species, which is the rat (63 ng·hr/mL, sexes combined). For doses with exposure above the NOAEL doses may be increased to give a maximum of 2-fold increase in exposure. Doses may also be decreased as appropriate. In cohorts in the next part of the study (Part 2), the doses may be increased as long as the maximum exposure multiplier is below 2-fold. The predicted steady state exposure in the MRD will not exceed the maximum exposure observed in the SRD.

All AEs reported during the Treatment Period, both within and across cohorts, up to the time of discharge on Day 5 (Part 1) and Day 10 (Part 2) will be evaluated to assess the need for subject and/or study termination in accordance with the prespecified criteria for discontinuation/termination (Section 6.3.1).

Following assessment of the AE data and pre-defined criteria for study termination, dose escalation may be interrupted/stopped and the blind broken for further analysis. Based on review of unblinded data, Takeda in consultation with the PI will decide if and how it is appropriate for the study to proceed.

If agreement regarding a dose escalation decision cannot be reached between the PI and Takeda, the study will be stopped.

# Figure 6.b Proposed Dose Escalation Scheme

## Part 1 SRD

Cohort $1 \rightarrow$	Cohort $2 \rightarrow$	Cohort 3→	Cohort 4→	Cohort $5 \rightarrow$	Cohort 6→	Cohort 7→	Cohort 8→	Cohort 9
(a)	(a)	(a)	(a)	(a)	(a)	(a)	(a)	(a)
0.1 mg	0.5 mg	2.5 mg	4.4 mg	8.8 mg	17.5 mg	35 mg	70 mg	105 mg
TAK-020 or	TAK-020 or	TAK-020 or	TAK-020 or	TAK-020 or	TAK-020 or	TAK-020 or	TAK-020 or	TBD
placebo	placebo	placebo	placebo	placebo	placebo	placebo	placebo	TAK-020 or
								placebo
Completed	Completed	Completed	Completed	Completed	Completed	Completed	Completed	

(a) Dosing with TAK-020 will progress to the next cohort after review of the safety, tolerability and PK data from the previous cohort and the agreement of the PI and Takeda of the next proposed dose.

TBD =to be determined for actual dose level when PK data from the previous cohort is available.

## Part 2 MRD

Part 2	Cohort $1 \rightarrow$	Cohort $2 \rightarrow$	Cohort 3→	Cohort 4→	Cohort $5 \rightarrow$	Cohort 6→	Cohort 7
MRD	3.75 mg	5.75 mg	13 mg	25 mg	X mg TBD	X mg TBD	X mg TBD
Evaluation	TAK-020 or	TAK-020 or	TAK-020 or	TAK-020 or	TAK-020 or	TAK-020 or	TAK-020 or
	placebo	placebo	placebo	placebo	placebo	placebo	placebo

TBD=to be determined for actual dose level when PK data from the previous cohort is available.

# 6.1.2 Criteria for Stopping Dose Escalation

- 1. Two or more subjects in any single cohort or across more than 1 cohort experience any of the Takeda Medically Significant List events (as outlined in Table 10.a).\*
- 2. Two or more subjects in any single cohort experience alanine aminotransferase (ALT) and/or aspartate aminotransferase (AST) elevations > 3 x upper limit of normal (ULN), irrespective of total bilirubin increase or other lab changes.
- 3. Two or more subjects in any single cohort or across more than 1 cohort experience ALT and/or AST elevations >5 × ULN in the absence of a concomitant bilirubin increase.\*
- 4. One or more subjects in any single cohort or across more than 1 cohort experience ALT and/or AST elevations >3 ×ULN in the presence of a total bilirubin increase >2 ×ULN or an international normalized ratio (INR) >1.5 without findings of cholestasis or other alternate etiology to explain the elevations (ie, "Hy's Law cases").
- 5. Two or more subjects in any single cohort or across more than 1 cohort experience ALT and/or AST elevations >3 ×ULN with the appearance of fatigue, nausea, vomiting, right upper quadrant pain or tenderness, fever, rash and/or eosinophilia (>5%).\*
- 6. Within each dose level, if 2 subjects develop a dose limiting toxicity (DLT) listed in Table 6.a that is confirmed by repeat test if applicable, the subject(s) will be unblinded prior to any dose-escalation safety review meeting. If the unblinded subjects have received TAK-020, no further dosing will occur in that dose level and no further dose escalation beyond that dose level will be allowed.
- 7. Two or more subjects in the same cohort experience the same toxicity graded at least as moderate ( $\geq$  Grade 2) and requiring discontinuation of investigational drug.

\* Please note that the study may be terminated early prior to full attainment of these criteria (eg, if just 1 subject experiences 1 of these events) if warranted by safety data from the other subjects dosed in the study to date.

- In addition to Takeda's standard criteria for study termination, the following stopping criteria will also be implemented in this study for individual subjects:
  - Within each dose level, if at least 1 subject develops a DLT listed in Table 6.a, and confirmed by repeat test, if applicable, the subject will be unblinded prior to any dose-escalation safety review meeting. If the unblinded subject has received TAK-020, no further dosing will occur in that subject.

Toxicity	Definition
Leukopenia	Total leukocyte count $<2500 \text{ cells/mm}^3$ (2.5×10  /L)
Neutropenia	Absolute neutrophil count $<1500/\text{mm}^3$ (1.5 x $10^9/\text{L}$ )
Thrombocytopenia	Platelet count $<75 \text{ x}10^9/\text{L}$
Lymphopenia	Lymphocyte count <1000 cells/mm  $(1.0 \times 10^9/L)$
Liver enzymes	ALT or AST $>3 \times$ ULN
Renal changes	Serum Creatinine>1.3×ULN
	Or
	eGFR decrease by 30% from Baseline
Abnormal coagulation	INR >2×ULN
	aPTT >2×ULN
	prothrombin time >2×ULN
QT interval with Fridericia correction method (QTcF)	QTcF >500 msec or a change from Baseline in QT/QTcF of >60 ms.
Severe infection	Serious infection requiring hospitalization, intravenous (IV) antibiotics (more than 1 dose), systemic antifungal or antiviral intervention

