# 6.3 Premature Termination or Suspension of Study or Investigational Site

# 6.3.1 Criteria for Premature Termination or Suspension of the Study

The study will be completed as planned unless one or more of the following criteria are satisfied that require temporary suspension or early termination of the study.

- New information or other evaluation regarding the safety or efficacy of the study medication that indicates a change in the known risk/benefit profile for TAK-020, such that the risk is no longer acceptable for subjects participating in the study.
- Significant violation of Good Clinical Practice (GCP) that compromises the ability to achieve the primary study objectives or compromises subject safety.
- Study meets predefined dose escalation stopping rules within or between cohorts and the sponsor and PI jointly decide not to study additional cohort(s) at a lower dose per Section 6.1.2.

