## 7.5 Criteria for Discontinuation or Withdrawal of a Subject

The primary reason for discontinuation or withdrawal of the subject from the study or study medication should be recorded in the eCRF using the following categories. For screen failure subjects, refer to Section 9.1.17.

- 1. Pretreatment event (PTE) or AE. The subject has experienced a PTE or AE that requires early termination because continued participation imposes an unacceptable risk to the subject's health or the subject is unwilling to continue because of the PTE or AE.
  - Liver Function Test (LFT) Abnormalities

Study medication should be discontinued immediately with appropriate clinical Follow-up (including repeat laboratory tests, until a subject's laboratory profile has returned to

normal/baseline status, see Section 9.1.8), if the following circumstances occur at any time during study medication treatment:

- ALT or AST  $> 8 \times$  ULN, or
- ALT or AST  $>5 \times$  ULN and persists for more than 2 weeks, or
- ALT or AST >3 × ULN in conjunction with elevated total bilirubin >2 × ULN or INR >1.5, or
- ALT or AST >3 × ULN with appearance of fatigue, nausea, vomiting, right upper quadrant pain or tenderness, fever, rash and/or eosinophilia (>5%).
- 2. Significant protocol deviation. The discovery postrandomization that the subject failed to meet protocol entry criteria or did not adhere to protocol requirements, and continued participation poses an unacceptable risk to the subject's health.
- 3. Lost to Follow-up. The subject did not return to the clinic and attempts to contact the subject were unsuccessful. Attempts to contact the subject must be documented.
- 4. Voluntary withdrawal. The subject (or subject's legally acceptable representative) wishes to withdraw from the study. The reason for withdrawal, if provided, should be recorded in the eCRF.

Note: All attempts should be made to determine the underlying reason for the withdrawal and, where possible, the primary underlying reason should be recorded (ie, withdrawal due to an AE).

- 5. Study termination. The sponsor, IRB, IEC, or regulatory agency terminates the study.
- 6. Pregnancy. The subject is found to be pregnant.

Note: If the subject is found to be pregnant, the subject must be withdrawn immediately. The procedure is described in Section 9.1.10.

7. Other.

Note: The specific reasons should be recorded in the "specify" field of the eCRF.

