## 10.2.3 Reporting of Abnormal LFTs

If a subject is noted to have ALT or AST elevated >3 ×ULN on 2 consecutive occasions, the abnormality should be recorded as an AE. In addition, an LFT Increases eCRF must be completed providing additional information on relevant recent history, risk factors, clinical signs and symptoms and results of any additional diagnostic tests performed. Concerning ALT/AST increases, please also see Section 6.1.2 Criteria for Stopping Dose Escalation.

If a subject is noted to have ALT or AST >3 ×ULN and total bilirubin >2 ×ULN for which an alternative etiology has not been identified, the event should be recorded as an SAE and reported as per Section 10.2.2. The investigator must contact the Medical Monitor for discussion of the relevant subject details and possible alternative etiologies, such as acute viral hepatitis A or B or other acute liver disease or medical history/concurrent medical conditions. Follow-up laboratory tests as described in Section 9.1.8 must also be performed. In addition, an LFT Increases eCRF must be completed and transmitted with the Takeda SAE form (as per Section 10.2.2).

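### Stopping criterion 3 no longer counts a subject with ALT/AST above 5×ULN once bilirubin rises, and gives no bilirubin threshold: a minor gap in the cross-cohort rule, closed by one phrase

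*Protocol*

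**What the plan says.** Protocol Section 6.1.2 has five criteria that can act on ALT or AST alone or with other findings:

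| Criterion | Subjects | Counted | ALT/AST | Further condition |
|---|---|---|---|---|
| 2 | 2 | one cohort only | >3×ULN | none; applies "irrespective of total bilirubin increase or other lab changes" |
| 3 | 2 | one cohort or across | >5×ULN | "ALT and/or AST elevations >5 × ULN in the absence of a concomitant bilirubin increase"; no threshold |
| 4 | 1 | one cohort or across | >3×ULN | counted only "in the presence of a total bilirubin increase >2 ×ULN or an international normalized ratio (INR) >1.5 without findings of cholestasis or other alternate etiology" |
| 5 | 2 | one cohort or across | >3×ULN | symptoms, fever, rash or eosinophilia |
| 6 | 2 | same dose level | >3×ULN (a DLT in Table 6.a) | confirmed by repeat test; unblinded and found to be on TAK-020 |

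Criterion 1 needs an event from Table 10.a, where a transaminase elevation by itself is not listed. Criterion 7 is limited to one cohort.

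Criteria 1, 3 and 5 carry a footnote: "the study may be terminated early prior to full attainment of these criteria (eg, if just 1 subject experiences 1 of these events". It depends on what the other subjects' safety data show.

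Two other sections put a number on bilirubin. Section 7.5 stops study drug for ALT or AST >3×ULN "in conjunction with elevated total bilirubin >2 × ULN or INR >1.5". Section 10.2.3 makes an SAE of "ALT or AST >3 ×ULN and total bilirubin >2 ×ULN for which an alternative etiology has not been identified". Neither is linked to criterion 3.

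Section 6.3.1 lists, among the grounds for suspending or ending the study, "Study meets predefined dose escalation stopping rules within or between cohorts", joined to a joint decision by the sponsor and PI not to study further cohorts at a lower dose.

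**The concern.** Any same-cohort pair above 5×ULN already meets criterion 2. Criterion 3 therefore adds a mandatory stop only for pairs in different cohorts, and that is where its bilirubin condition removes subjects. Criterion 4 does not pick up every subject removed: it needs bilirubin above 2×ULN (or INR above 1.5) with no cholestasis or other explanation. The result runs the wrong way. A pair with normal bilirubin must stop escalation, while the same pair with a higher bilirubin in one subject need not.

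The liver matters in this trial. Section 6.2 reports rat liver toxicity at an AUC of 431 ng·h/mL or more, and Section 6.1.1 escalates towards an unbound AUC about twice that at the rat LOAEL. A count that fails to register also does not reach the termination ground in Section 6.3.1.

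**Working it through.** The plan states no figure to reproduce, so the check is of the rule logic.

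**1. States.** Take a subject with ALT/AST >5×ULN, INR not above 1.5, no criterion 5 features and no criterion 1 or 7 event. Total bilirubin is in one of four states:

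- A: up to ULN
- B: above ULN, up to 2×ULN
- C: >2×ULN, unexplained
- D: >2×ULN, with cholestasis or another etiology

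**2. Which criterion counts each state.** Criterion 4 is met by C alone. Criterion 3 counts A on the literal reading (increase = above ULN), or A and B if increase means >2×ULN. Counted by neither: B and D (2 of 4) literally; D (1 of 4) on the >2×ULN reading.

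**3. Pairs at different dose levels.** Four states give 4×5/2 = 10 unordered pairs. Four contain C (AC, BC, CC, CD) and meet criterion 4. The other six are AA, AB, AD, BB, BD and DD.

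| Reading | Stopped by criterion 3 | Meets no criterion |
|---|---|---|
| Literal (above ULN) | AA | AB, AD, BB, BD, DD: 5 of 10 |
| >2×ULN | AA, AB, BB | AD, BD, DD: 3 of 10, each with a D |
| Criterion 3 irrespective of bilirubin | all six | none: 0 of 10 |

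Pairs in the same cohort: 0 of 10 missed (criterion 2). Pairs at the same dose, confirmed and both on TAK-020: 0 of 10 missed (criterion 6).

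**4. Example (pair AB).** At two dose levels, one subject has ALT 6×ULN with normal bilirubin and the other has ALT 6×ULN with bilirubin 1.5×ULN. Both have INR not above 1.5, and not both have symptoms. Literally, criterion 3 counts one subject. Criterion 4 fails because 1.5 < 2, criterion 5 because it needs two subjects with features, and criteria 2, 6 and 7 because cohort and dose differ. With normal bilirubin in both, criterion 3 stops escalation.

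**5. Dependence on the partition.** A finer grid uses 4 bilirubin levels (none, rise within normal, ULN to 2×ULN, >2×ULN) × INR above 1.5 or not × explained or not × symptoms or not. That is 32 profiles and 32×33/2 = 528 pairs. Missed: 130 (24.6%) if increase means above ULN and 61 (11.6%) if it means >2×ULN. With no explanation in either subject: 8 and 0. If criterion 3 ignored bilirubin: 0. The fractions move with the grid, so they show where the gap lies and not how large it is.

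**6. Reach.** Figure 6.b leaves only MRD cohorts 5 to 7 with doses to be set, and seven is the maximum. Assume no earlier case above 5×ULN; Section 6.2 calls the tested doses safe and well tolerated, which suggests this but does not state it. Of the cohort pairs (5,6), (5,7) and (6,7), only (5,6) precedes a remaining escalation: 1 decision, 1×6 = 6 subjects on TAK-020. If one earlier case exists, a second in cohort 5 or 6 affects at most 2 decisions, 2×6 = 12 subjects on TAK-020.

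**The case against.** The case against giving this weight is strong.

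- **The reading.** Criterion 4, the next item, gives its bilirubin increase a limit of >2×ULN, and Sections 7.5 and 10.2.3 use the same limit. That is the more natural reading of criterion 3. On it, no pair is missed unless one subject's bilirubin has another explanation, and leaving explained cases to case review is defensible.
- **The safeguards.** Under Section 11.0 all sponsor representatives and the PI must agree on the next dose, and any one person can veto. Under Section 6.1.1 the study stops if the PI and sponsor disagree. Each confirmed ALT/AST >3×ULN is a DLT, unblinded before the escalation meeting, with no further dosing for that subject if on TAK-020. Section 7.5 stops drug at bilirubin >2×ULN with no etiology exception. Section 6.3.1 also acts on a change in risk "such that the risk is no longer acceptable for subjects participating in the study". In 2 of the 5 literal patterns (AB, AD) and 2 of the 3 others (AD, BD), one subject is already a criterion 3 event, so the note's one-subject example applies directly.
- **The wider count.** Criterion 3 has no unblinding step, so counting irrespective of bilirubin would also count explained or placebo cases.

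Most of this stands, and it limits the weight of the point. Two things do not fall away. The text gives no number, so a literal reader is not misreading it. And criterion 3 has no etiology or treatment exception: it already counts an explained or placebo case while bilirubin is normal, and drops that case when bilirubin rises. The safeguards are discretionary or act on single subjects, so they do not replace the count.

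**Conclusion.** A minor, cheap improvement. The gap is real on the text but narrow. It needs two subjects above 5×ULN at different dose levels, neither meeting criterion 4, not both with criterion 5 features, no other criterion met, and at least one in an uncounted bilirubin state. Whether state B is part of the gap depends on the reading of *increase*; state D is part of it on either reading. Step 6 bounds the reach, given the doses fixed in Amendment 4.

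Three stronger conclusions might be inferred, and the documents do not support them:

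- *Unexplained liver injury with bilirubin above 2×ULN is missed.* It is not: criterion 4 stops escalation on one such subject, from ALT/AST >3×ULN.
- *Escalation would go ahead in the gap.* Nothing makes it automatic; what is missing is a mandatory stop. Even meeting a stopping rule leads to termination under Section 6.3.1 only with a further joint decision.
- *The pair fractions measure the risk.* They count logical patterns, and the documents give no rate from which a likelihood could be formed.

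**What to change.** In criterion 3, replace the bilirubin condition with the phrase criterion 2 already uses, "irrespective of total bilirubin increase or other lab changes". Criterion 4 stays as the stricter one-subject rule. The ALT/AST limits, the note and the review process do not change.

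Defining the increase as total bilirubin >2×ULN would be the lesser change. It settles the reading but adds no stop beyond the natural one, and pairs with an explained case stay uncounted (3 of 10 in step 3).

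The cost is one phrase in Section 6.1.2, by amendment, with no new data, staff or procedures. The downside is a rare extra stop, sometimes for an explained or placebo case. Given the small effect, the change could go into the next amendment made for another reason.

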#### 7.4 **Diet, Fluid, and Activity Control**

Subjects will be confined to the clinic for the duration of each treatment period: Part 1, Day -1 through Day 5, Part 2, Day -1 through Day 10.

TAK-020	
Study No. TAK-020-1001	Page 37 of 101
Protocol Incorporating Amendment No. 4.0	27 March 2017

During the confinement period, subjects will be given a menu for the dosing period that includes 3 meals and an evening snack, each containing approximately 30% fat (relative to the total calories). On dosing days, breakfast will not be served. For Part 1 of the study, the meals served on the day of dosing should be identical for each cohort in the study. For Part 2 of the study, meals served on the PK assessment days (Days 1 and 9) should be identical for each cohort, M eals on other days should be standardized to ensure comparability if options are provided (consistent protein, carbohydrates, and fat content).

The study menu should be recorded and submitted to the study file with a copy provided to the sponsor prior to the start of the study. The meal start and stop times and percentage of the meal consumed will be recorded in the source and appropriate eCRF for all meals served on PK assessment days, Day 1 for Part 1 of the study (SRD), and Days 1 and 9 for Part 2 of the study (MRD).

If a blood draw or any study procedure coincides with a meal, the blood draw will take precedence followed by the study procedure and then the meal.

During the SRD arm of the study, Part 1, TAK-020 and placebo will be administered on Day 1 with 240 mL of water after a fast of at least 10 hours. Subjects will continue to fast for an additional 4 hours after dosing. Subjects may consume water ad libitum with the exception of 1 hour before and 1 hour after drug administration.

During the MRD arm of the study, Part 2, TAK-020 and placebo will be administered on Days 1 and 3 through 9 with 240 mL of water after a fast of at least 10 hours. Subjects will continue to fast for an additional 4 hours after dosing. Subjects may consume water ad libitum with the exception of 1 hour before and 1 hour after drug administration. The dosing regimen and diet should be consistent on each day of the study.

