## **11.0 STUDY-SPECIFIC COMMITTEES**

No steering committee, data safety monitoring committee, or clinical endpoint committee will be used in this study.

Takeda (at a minimum, the clinical science representative(s) and pharmacovigilance physician) and the PI will review the safety and tolerability data, pharmacokinetic data for each cohort prior to dosing any additional cohort. The decision for the next subsequent dose must be agreed by all representatives of Takeda and the PI. If any one person has concerns regarding subsequent dosing, this acts as veto and the decision not to proceed with an additional cohort will be escalated to management.

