## 13.2 Interim Analysis and Criteria for Early Termination

No interim analysis is planned. Section 6.1.1 describes the blinded safety and PK review which will take place after completion of each cohort and prior to the next dose escalation stage in the study.

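### The DLT rules in Protocol 6.1.2 do not require dosing to stop before the next scheduled Part 2 dose, except where the liver patterns of 7.5 apply

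*Protocol*

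**What the plan says.** Protocol 6.1.2 has two rules based on the DLTs in Table 6.a.

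- **Individual subject.** A subject with a DLT, confirmed by repeat test if applicable, is to be "unblinded prior to any dose-escalation safety review meeting. If the unblinded subject has received TAK-020, no further dosing will occur in that subject".
- **Criterion 6.** If two subjects at a dose level have a confirmed DLT, "the subject(s) will be unblinded prior to any dose-escalation safety review meeting". If they received TAK-020, dosing at that level ends and escalation beyond it is barred.

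Neither rule names a day. On when the meeting takes place, section 13.2 states: "Section 6.1.1 describes the blinded safety and PK review which will take place after completion of each cohort". Section 11.0 says that the sponsor and the principal investigator "will review the safety and tolerability data, pharmacokinetic data for each cohort prior to dosing any additional cohort".

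In Part 2, section 7.4 states that "TAK-020 and placebo will be administered on Days 1 and 3 through 9".

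Table 6.a covers cytopenias, ALT or AST above 3 x ULN, renal changes, coagulation, severe infection and QTcF ("QTcF >500 msec or a change from Baseline in QT/QTcF of >60 ms"). Section 7.5 has its own liver rule: "Study medication should be discontinued immediately with appropriate clinical Follow-up" if ALT or AST

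- exceeds 8 x ULN;
- exceeds 5 x ULN "and persists for more than 2 weeks";
- exceeds 3 x ULN with raised bilirubin or INR; or
- exceeds 3 x ULN with listed symptoms or signs.

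**The concern.** The individual-subject rule is there to stop dosing in someone who has reached a predefined toxicity limit. Part 1 is a single dose, so the rule can act only in Part 2. It acts only after unblinding, and the only stated deadline for unblinding appears to fall when no Part 2 dose is left. A site could follow the rule to the letter and still give every remaining dose.

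The subjects exposed to this are those in Part 2 Cohorts 5 to 7, if they are opened. They are healthy volunteers, and their doses were still to be set at Amendment 4. Section 6.2 allows unbound exposure above twice that at the rat LOAEL, where liver toxicity was seen. It also treats rat kidney changes as irreversible because recovery was not tested.

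**Working it through.** **Step 1: dose count.** Section 7.4 gives Day 1 and Days 3 to 9, so 1 + 7 = 8 doses. This reproduces the maximum of 8 days in the Study Summary.

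**Step 2: what is left at the stated deadline.** If the meeting follows cohort completion (13.2), it follows the Day 9 dose, and 0 of 8 doses remain.

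**Step 3: doses remaining after a laboratory DLT.** Appendix A schedules on-treatment laboratory tests on Days 2, 3, 5 and 8. Table 9.d lists a safety sample on Days 2, 3 and 5 but none on Days 6 to 8, so Day 8 is uncertain. Let d be the day of the first qualifying value and k the days to a repeat result. The documents do not give k, so 1 and 2 are assumed. The doses remaining are the dose days later than d + k if that day's dose has already been given, or from d + k onwards if the result is acted on predose.

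| First value (d) | k = 0 (first value) | k = 1 | k = 2 |
|---|---|---|---|
| Day 2 | 7 | 6-7 | 5-6 |
| Day 3 | 6-7 | 5-6 | 4-5 |
| Day 5 | 4-5 | 3-4 | 2-3 |
| Day 8 (Appendix A only) | 1-2 | 0-1 | 0 |

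Example: d = 5 and k = 1 gives confirmation on Day 6. Days 7, 8 and 9 remain (3 doses), or Days 6 to 9 (4 doses). Both rules act on a confirmed DLT where a repeat applies, so k = 1 and k = 2 are the relevant columns.

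**Step 4: QTcF.** Section 9.1.11.1 schedules ECGs over the 24 hours after the Day 1 dose and predose on Days 3, 5 and 9. If the repeat ECG is done at once, before any further dose, 7 doses remain after a Day 1 postdose finding. For the predose ECGs on Days 3, 5 and 9, 7, 5 and 1 remain.

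**Step 5: do other sections require a stop?**

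- *7.5, liver.* The two-week pattern cannot be met during dosing: Day 1 + 14 days = Day 15, after Day 9. The other three can. Isolated ALT/AST above 3 and up to 8 x ULN is therefore a DLT with no mandatory stop.
- *7.5 (adverse event category) and 7.6.* These rest on a judgement of unacceptable risk, and 7.6 is permissive.
- *6.1.1.* Adverse events up to Day 10 must be evaluated for the need to terminate a subject. This is a duty to evaluate, with no hold attached. Under 10.1.3 a laboratory or ECG change is an adverse event only if judged clinically significant. ALT/AST above 3 x ULN on two consecutive occasions is one automatically (10.2.3).
- *8.5.* Drug stops and the subject is withdrawn once site personnel are unblinded, but this depends on the same undated unblinding. The section also restricts the investigator to breaking the blind for medical treatment.
- *7.5 and 9.1.10.* Pregnancy requires a stop but is not a DLT.

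**Step 6: subjects concerned.** Section 6.2 reports the first four Part 2 doses as already tested. Cohorts 5 to 7 would give 3 x 8 = 24 subjects, of whom 3 x 6 = 18 are on TAK-020.

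**Step 7: renal margin.** Section 6.2 gives protein binding of 98.9% in humans and 98.0% in rats. Human exposure cap: 1808 x 0.011 = 19.9 ng*h/mL unbound, matching the plan's figure. Rat kidney toxicity: 2030 x 0.020 = 40.6 ng*h/mL unbound. Ratio: 19.9 / 40.6 = 0.49.

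**The case against.** The strongest reply is that the harm needs a reading that empties the rule. A stopping criterion for individual subjects makes sense only if unblinding comes while doses remain, so the meeting is best read as an outer limit that ensures reviewers know the assignment. That is probably the intent. The timing of the meeting is itself inferred from 13.2 and 11.0, since 6.1.2 gives no day. Subjects are confined and dosed under supervision, laboratory reports must be reviewed and signed, and adverse events must be evaluated during treatment. A competent investigator would normally stop. A subject hospitalised for infection would in practice miss doses, because dosing takes place only in the clinic. All of this stands, and it makes the counts ceilings. It does not supply a requirement.

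The renal argument is also weaker than it first looks. The exposure cap is about half the unbound level at which rats showed kidney toxicity, that rat study lasted 4 weeks, and section 6.2 provides for kidney markers to be monitored. The irreversibility statement is a cautious assumption made for lack of data.

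Finally, a hold from the first unconfirmed value is open to fair objection. The blood-count DLTs are absolute cut-offs, while exclusion 18 sets a numeric laboratory limit only for ALT/AST. A subject with a low but stable count could be held without any change from Baseline.

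**Conclusion.** The concern holds as a gap in what the protocol requires, and it should be closed before further Part 2 cohorts are dosed. For a confirmed DLT outside the attainable 7.5 liver patterns, nothing obliges the site to stop before the next scheduled dose. With a repeat test assumed to take 1 day, up to 6-7, 5-6 or 3-4 of 8 doses remain after a Day 2, 3 or 5 laboratory finding. With 2 days, it is 5-6, 4-5 or 2-3. Confidence is medium, because the result rests on the inferred meeting date and the assumed repeat time.

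Three stronger readings might be inferred, and the documents do not support them:

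- *That the protocol directs dosing to continue until the meeting.* It does not. Earlier unblinding and stopping are open throughout.
- *That nothing else can force a stop.* The three attainable liver patterns, pregnancy and unblinding of site personnel all do, and 6.1.1 requires evaluation for subject termination.
- *That the DLT rules have no effect.* Criterion 6 still bars escalation and further use of the dose level.

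**What to change.** Amend 6.1.2 as follows.

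1. Once a Table 6.a DLT is confirmed, or at once where no repeat test applies, the subject receives no further dose until unblinded.
2. Unblinding takes place before that subject's next scheduled dose. For criterion 6, it takes place before the cohort's next scheduled dose.
3. The meeting deadline is kept only for the escalation decision.
4. Section 8.5 is cross-referenced so that this unblinding is expressly permitted.

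Holding from the first unconfirmed value is optional and can be left to the sponsor.

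The cost is a few sentences in an amendment and a note to the site. The unblinded pharmacist and sealed envelopes already exist (8.4). The downside is an occasional missed dose, or a withdrawal under 8.5 if site personnel are unblinded. That subject may be on placebo: 2 of 8 per cohort, so a 25% chance if the DLT is unrelated to drug. If the subject is on TAK-020, Day 9 PK may be lost for 1 of the 6 active subjects in that cohort, which weakens its Day 9 versus Day 1 comparison.
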